10.3. Vital Signs

Actual values and changes from baseline in clinical laboratory test results will be summarized by treatment at each time point using descriptive statistics (number of subjects, mean, standard deviation [SD], median, minimum, and maximum). Vital signs (systolic blood pressure [SBP] and diastolic blood pressure [DBP], oral body temperature, respiratory rate, and heart rate [HR]) results will be presented in a data listing sorted by treatment group, subject, and collection date/time. Actual results and change from baseline will be summarized for the Safety Population.

10.4. Electrocardiogram (ECG)

Twelve-lead ECGs will be obtained after the subject has rested in the supine position for ≥ 10 minutes or as clinically indicated based on reported AEs or laboratory findings, as necessary.

Electrocardiogram assessments will include comments concerning whether the tracings are normal or abnormal, rhythm, presence of arrhythmia or conduction defects, morphology, and any evidence of MI, or ST-segment, T-Wave, and U-Wave abnormalities. In addition, measurements of these intervals will be reported: HR, PR interval, QRS duration, QT interval, Fridericia-corrected QT interval (QTcF), and RR interval. The investigator will determine whether any of the 12-lead ECG results are CS or NCS.

If both QT and RR intervals are not missing, but QTcB interval is missing in the database the Bazett's-corrected QT interval (QTcB) measured in msec will be calculated using the formula below, where RR interval is measured in msec:

$$\bullet \quad QTcB = \frac{QT}{\sqrt{RR/1000}}$$

If both QT and RR intervals are not missing but QTcF interval is missing in the database, QTcF measured in msec will be calculated using the formula below, where RR interval is measured in msec:

$$\bullet \quad QTcF = \frac{QT}{\sqrt{RR/1000}}$$

Electrocardiogram results will be presented in data listing sorted by treatment group, subject, and date/time of assessment. Actual results and change from baseline will be summarized for the safety

population at each timepoint using descriptive statistics. All ECG results will be presented in a data listing.

In addition, subjects with outlying QTcF, and QTcB intervals (absolute value > 500 msec, absolute value > 480 msec, absolute value > 450 msec, or increase from baseline value >30 or >60 msec) will be listed in a separate data listing. A summary table will be presented for maximum QTcF and QTcB intervals (including scheduled and unscheduled assessments) meeting the outlying criteria using count and percentage.

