6.1.1.5 Standard Vital Signs

Vital signs will be measured at the time points indicated in the Schedule of Events (Appendix 3). Vital sign measurements will include SBP, DBP, body temperature, RR, and HR. The subject will have rested in a supine position for ≥ 10 minutes before all measurements are taken.

Note: Vital signs collected during the initial 60 minutes of infusion of study drug require only the SBP, DBP and HR.

The Investigator will determine whether any of the vital sign measurements are clinically significant (CS) or not clinically significant (NCS). Clinical significance is defined as any variation in results that has medical relevance and may result in an alteration in medical care (e.g., active observation, diagnostic measures, therapeutic measures). If a CS change from Screening values is noted, the CS value and reason for clinical significance will be documented on the AE page of the eCRF. The Investigator will continue to monitor the subject with additional assessments until the value has reached either the reference range or the value at Screening or until the Investigator determines follow-up is no longer medically necessary.

6.1.1.6 12 Lead Electrocardiogram

Twelve-lead ECGs will be obtained after the subject has rested in the supine position for ≥ 10 minutes at scheduled timepoints or as clinically indicated based on reported AEs or laboratory findings, as necessary.

The Investigator should review and sign the ECG for any immediate issues.

Electrocardiogram assessments will include comments concerning whether the tracings are normal or abnormal, rhythm, presence of arrhythmia or conduction defects, morphology, and any evidence of MI, or ST-segment, T-Wave, and U-Wave abnormalities. In addition, measurements of these intervals will be reported: RR interval, PR interval, QRS width, and uncorrected QT, QTcB, QTcF. The Investigator will determine whether any of the 12-lead ECG results are CS or NCS.

Clinical significance is defined as any variation in results that has medical relevance and may result in an alteration in medical care (e.g., active observation, diagnostic measures, therapeutic measures). If a CS change from Screening is noted, the CS value and reason for CS will be documented on the AE page of the eCRF. The Investigator will continue to monitor the subject with additional assessments until either the values have reached either reference range or the

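### As printed, the SAP's fallback formula for a missing QTcF uses the square root and equals the QTcB formula, so any derived QTcF would be a Bazett value labelled Fridericia

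*SAP*

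**What the plan says.** SAP Section 10.4 gives two fallback derivations, one after the other.

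- For Bazett: "Bazett's-corrected QT interval (QTcB) measured in msec will be calculated using the formula below". In the typesetting notation of the extracted text (closing braces cut) the formula begins "QTcB = \frac{QT}{\sqrt{RR/1000".
- For Fridericia: "If both QT and RR intervals are not missing but QTcF interval is missing in the database", then "QTcF measured in msec will be calculated using the formula below, where RR interval is measured in msec". The formula begins "QTcF = \frac{QT}{\sqrt{RR/1000".

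The QTcF formula is a fallback only. The same section lists among the reported measurements the "Fridericia-corrected QT interval (QTcF), and RR interval", and Protocol Section 6.1.1.6 has both corrected intervals recorded: "measurements of these intervals will be reported: RR interval, PR interval, QRS width, and uncorrected QT, QTcB, QTcF".

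QTcF and QTcB then feed a listing of outlying values, with the criteria "absolute value > 500 msec, absolute value > 480 msec, absolute value > 450 msec, or increase from baseline value >30 or >60 msec", and a table of counts and percentages for each subject's maximum. Neither output separates recorded from derived values.

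**The concern.** Two differently named corrections cannot share one formula. Dividing by the square root of RR in seconds is Bazett's correction; Fridericia's divides by the cube root. Neither document prints a cube-root expression, so a programmer who follows Section 10.4 literally would fill each missing QTcF with the Bazett value.

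What is at stake is the QTcF safety summary. The two corrections agree only at 60 bpm. Above that rate the printed formula overstates QTcF and can create false outliers; below it, the formula understates QTcF and can hide true ones. A recorded Fridericia baseline set against a derived post-dose value would also show a change that did not happen. Protocol Section 5.3 applies a QTcF limit of 450 ms at Screening/Check-in or Day 1, so a pre-dose QTcF is likely to be on record, which makes this mixed comparison the more plausible one.

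**Working it through.** The plan states no figure to reproduce. The check compares the printed formula with the cube-root form.

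**Inputs**
- Printed QTcF: QT/(RR/1000)^(1/2), RR in ms (SAP 10.4).
- Fridericia: QT/(RR/1000)^(1/3).
- Heart rate (HR) 50 to 100 bpm, the eligibility limits in Protocol 5.3. With RR = 60000/HR this is RR 1200 to 600 ms.
- QT values and the true QTcF of 420 ms are illustrative assumptions, not figures from the documents.

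**Step 1: relative error.** Printed / cube-root = (RR/1000)^(-1/6), whatever the QT.

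| HR | RR (ms) | Ratio | QT 400: printed | QT 400: cube root |
|---|---|---|---|---|
| 50 | 1200 | 0.970 | 365.1 | 376.4 |
| 60 | 1000 | 1.000 | 400.0 | 400.0 |
| 75 | 800 | 1.038 | 447.2 | 430.9 |
| 80 | 750 | 1.049 | 461.9 | 440.3 |
| 100 | 600 | 1.089 | 516.4 | 474.3 |

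**Step 2: examples with QT varied with rate (assumed).**
- HR 90, QT 370: 370/0.8165 = 453 ms printed; 370/0.8736 = 424 ms by cube root. Inflation about 30 ms.
- HR 100, QT 355: 355/0.7746 = 458 ms printed; 355/0.8434 = 421 ms by cube root. Inflation about 37 ms.
- HR 50, QT 440: 440/1.0954 = 402 ms printed; 440/1.0627 = 414 ms by cube root. Understated by about 12 ms.

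The first two are flagged as above 450 ms when the Fridericia value is not. They exceed 450 by about 3 and 8 ms; the 30 and 37 ms are the distances from the cube-root values.

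**Step 3: where the absolute limits effectively move.** The true QTcF at which the printed value reaches a limit is limit × (RR/1000)^(1/6).

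| HR | 450 limit | 480 limit | 500 limit |
|---|---|---|---|
| 50 | 463.9 | 494.8 | 515.4 |
| 75 | 433.6 | 462.5 | 481.7 |
| 100 | 413.3 | 440.8 | 459.2 |

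**Step 4: spurious change.** Take a recorded Fridericia baseline of 420 ms, then a derived post-dose value with no true change. The apparent increase is 420 × [(HR/60)^(1/6) − 1], where HR is the post-dose rate:
- HR 70: 10.9 ms
- HR 80: 20.6 ms
- HR 90: 29.4 ms
- HR 100: 37.3 ms

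The 30 ms criterion is crossed when (HR/60)^(1/6) exceeds 450/420 = 1.0714, that is, when HR exceeds 60 × 1.0714^6, about 91 bpm.

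**Step 5: the 60 ms criterion.** At HR 100 and a recorded baseline of 450 ms, the formula adds 450 × 0.0889 = 40 ms. The formula alone does not reach 60 ms in this comparison.

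**The case against.** **The root index may have been lost in reading.** On the page, a square root and a cube root differ by one small digit on the radical. The same extracted text garbles a subscript in the alternative PRU formula of SAP 9.1, and drops the day number from the ticagrelor footnote of Protocol Table 1 that Appendix 3 retains. Printing two formulas under two names suggests that two expressions were meant. This stands as a real possibility, though it is not shown; if the source page carries the index, the formula point falls away.

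**The intended method is clear by name.** SAP 10.4 and the protocol's abbreviation list both call QTcF Fridericia-corrected, so a careful programmer might query the duplicate. That lowers the chance of silent use, but the printed expression is still the only computational instruction.

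**QTcF is expected to be recorded.** A reader might infer that the whole QTcF outlier table would hold Bazett values. The documents do not support that: the formula applies only where QTcF is missing, both documents list QTcF as a reported measurement, and no missing rate is given. The table would be wholly Bazett only if QTcF were never recorded. Against this, Protocol 6.1.1.6 has each site supply its own ECG machine unless the sponsor does, 5 to 15 sites are planned, and the SAP itself provides for missing QTcF, so the fallback cannot be assumed idle.

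**The examples are chosen.** The larger errors sit near the top of the eligible heart-rate range. That is fair. The direction and percentage error do not depend on the assumed QT, but whether a limit is crossed does.

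**Conclusion.** The point holds for the text available, subject to a check of the source page. Any QTcF derived under SAP 10.4 would equal QTcB: about 3% too low at 50 bpm, 3.8% too high at 75 and 8.9% too high at 100. To the extent that such values enter the listing and the maximum-QTc table, they can be misclassified in either direction against 450, 480 and 500 ms. They can also be misclassified against the 30 ms change limit when a recorded baseline meets a derived post-dose value.

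The sizes rest on assumed QT and QTcF values and on heart rates within the eligibility limits, which need not bound post-dose rates. How many records are affected cannot be estimated from the documents. It would go too far to conclude that the outlier table as a whole is invalid, or that the formula alone would turn an unchanged recorded baseline of up to 450 ms into an increase above 60 ms at these rates. The outputs concerned are descriptive safety summaries; the primary endpoint, its test and the sample size are untouched. The formula should be settled before database lock.

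**What to change.** 1. Check the QTcF formula on the source page of SAP 10.4. If the cube-root index is there, the formula needs no change.
2. If it is absent, print QTcF = QT/(RR/1000)^(1/3), with QT and RR in ms.
3. Add a sentence that derived QTc values will be flagged in the QTc listing and identified in the outlier table, so that mixed recorded and derived comparisons can be seen.

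The cost is one formula, one sentence and a flag variable in the ECG dataset, with no change to data collection. Recomputing QTcF from QT and RR for every ECG would give one method throughout, but it is optional: it replaces the plan's use of recorded values and could make analysed values differ from those used for eligibility.

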10.5. Physical Exams

Physical exam results are collected at the screening visit only. These will be presented in a listing.

11. PHARMACOKINETIC ANALYSIS

The ticagrelor and TAM pharmacokinetic results will be analyzed for all randomized subjects, and the PB2452 results will be analyzed for the PK Population.

Plasma Concentrations

Plasma concentrations will be listed by nominal timepoints and subject, and summarized descriptively (number of subjects, mean, SD, coefficient of variation [CV], geometric mean, geometric CV, median, minimum, and maximum). Plasma concentration versus time profiles for each subject will be presented graphically. The mean plasma concentration versus time profiles will be presented graphically both on the linear and semi-log scale. All concentration plots will be presented using nominal times from the time of PB2452 dosing.

Plasma concentration values below the limit of quantification (BLQ) will be set to zero for calculation of all summary statistics except for geometric mean and geometric CV. In case any value is BLQ, the geometric mean and geometric CV will be presented as NA. For the semi-log plots if the mean value is zero (i.e., if all values are BLQ at a timepoint) then it will be set to LLOQ/2 in the plot.

Scatter plots of pharmacokinetic data versus total and unbound PB2452 plasma concentrations may be prepared for including both treatment groups with placebo group concentration set to zero.

Plasma Pharmacokinetic Parameters

Plasma pharmacokinetic parameters of PB2452, ticagrelor, and TAM will be determined using noncompartmental models using Phoenix WinNonlin Version 8.1 or higher and summarized by time point using descriptive statistics (number of subjects, mean, SD, CV, median, minimum, and maximum). In addition, geometric means and geometric CVs will be reported for AUCs and Cmax. Actual sampling times, rather than scheduled sampling times, will be used in all calculations of PK parameters.

For calculating the PK parameters, BLQ values will be treated as zero with the exception that a BLQ value between 2 quantifiable concentrations will be set as missing. If 2 or more consecutive BLQ concentrations are followed by quantifiable concentrations in the terminal phase, those concentrations after BLQ concentrations will be treated as missing. Missing concentrations will not be imputed for calculating the PK parameter.

The terminal elimination phase will be identified by regression analysis using logarithmically transformed plasma concentrations. An elimination phase will be considered invalid for the following situations:

- It has less than 3 data points;
- It has a positive slope (or correlation coefficient $[r]>0$);
- Adjusted $r^2 \leq 0.8$. (Adjusted $r^2 = 1 - \{(1-r^2) \times (n-1)\} / (n-2)$, where n is the number of data points in the regression and r^2 is the square of the correlation coefficient.).
- In cases where $C_t/\lambda z$ (i.e., the extrapolated portion of $AUC_{0-\infty}$) is $\geq 20\%$ of $AUC_{0-\infty}$, $AUC_{0-\infty}$ will be considered invalid.

Urine PK Concentration

Pooled urine samples to assess urine PB2452, ticagrelor and TAM concentrations will be collected over the following intervals: before dosing (within 60 minutes prior to the first ticagrelor dose on Day -2) and 0 to 6, 6 to 12, and 12 to 24 hours post dose.

For PB2452 concentration, urine concentration will be summarized by the time-intervals mentioned above. For Ticagrelor and TAM concentrations, the summary will be presented by treatment.

For each analyte, urine concentration and volume data will be listed by collection interval for each subject.

Urine Parameters

The urine PK parameters Ae_{24} , Ae_{48} , and Ae_{t1-t2} (for 0 to 6, 6 to 12, 12 to 24 and 24 to 48 hours), Fe_{48} , and CL_r for PB2452, ticagrelor and TAM in urine will be listed by subject and summarized for using descriptive statistics (number of subjects, mean, SD, CV, median, minimum, and maximum).

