2.1.2.2 Justification for Dosing Strategy

In the first in human Phase 1 study of PB2452, 18 g administered as an initial 6 g bolus followed by a prolonged infusion of the remaining 12 g over 16 hours in healthy subjects aged 18-50 years old provided immediate and sustained reversal of the antiplatelet effects of ticagrelor and was considered generally safe and well tolerated. Significant reversal was observed by 5 minutes after initiation of infusion and was sustained for 20-24 hours. This profile of rapid and sustained ticagrelor reversal delivered by the 18 g infusion of PB2452 is considered ideal for patients on ticagrelor with uncontrolled major or life-threating major bleeding or who need urgent or invasive surgery. Importantly, there were no PB2452-related adverse effects, infusion-related

Clinical Study Protocol PB2452-PT-CL-0003-Phase 2b Version 2 dated 28May2021

reactions (IRRs), or dose-limiting toxicities (DLTs) observed as determined by the study Investigator and safety review committee (SRC) of the Phase 1 study. The 18 g dose level and 16-hour infusion regimen administered in the Phase 1 study was repeated in a Phase 2A (PB2452-PT-CL-0002) clinical study of PB2452 in older (50-64 years old) and elderly (65-80 years old) subjects pretreated with DAPT for 48 hours. This population is similar in age and background comorbidities to the target patient population treated with ticagrelor as part of DAPT for prior heart attack or recent coronary stent placement. Preliminary data indicate that the reversal and safety profiles in the Phase 2A population pretreated with DAPT was similar to the results observed in the Phase 1 study.

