2.1.3 Supportive Nonclinical Data

Non-clinical pharmacology studies have demonstrated that PB2452 binds with high affinity and selectivity to the P2Y₁₂ receptor antagonist ticagrelor and its active metabolite, TAM, (equilibrium dissociation constant [K_D] 20 pmol/L). PB2452 rapidly neutralizes the unbound plasma fraction of ticagrelor and TAM, thereby reversing ticagrelor- and TAM-mediated inhibition of adenosine diphosphate (ADP)-induced platelet aggregation in a concentration- and dose-dependent manner in vitro (in human platelet-rich plasma) and in vivo (mouse and pig, dose-dependency data in mouse only). In mice dosed with ticagrelor to a supratherapeutic plasma exposure, those dosed with PB2452 administration prior to a tail cut had reduced bleeding to a degree comparable and not statistically different from the observation in mice not treated with ticagrelor (Buchanan, 2015).

The non-clinical pharmacology profile of PB2452 supported further exploration of the use of this compound as a novel ticagrelor antidote therapy. Detailed descriptions of the non-clinical pharmacology of PB2452 may be found in the Investigators' Brochure (IB) for PB2452.

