3.2. Endpoints

Hypothesis

Compared to placebo, PB2452 administered intravenously provides rapid and sustained reversal of the antiplatelet effects of ticagrelor.

Primary Endpoint

- The primary efficacy endpoint is the minimum % inhibition of PRU assessed by VerifyNow within 4 hours after the initiation of study drug. Percent inhibition of PRU is calculated as $100 * [(PRU_{bsl} - PRU_{trt})/PRU_{bsl}]$ where PRU_{bsl} refers to the PRU value measured before treatment with ticagrelor and PRU_{trt} refers to the PRU value measured posttreatment with the study drug.

Secondary Endpoints

- Safety, tolerability and immunogenicity will be assessed by monitoring and recording of adverse events (AEs), including infusion site and systemic infusion reactions, clinical laboratory test results (hematology, coagulation, serum chemistry, and urinalysis), vital sign measurements (systolic and diastolic blood pressures, oral body temperature,

respiratory rate, and heart rate), 12 lead electrocardiogram (ECG) results, physical examination findings, and immunogenicity.

- Plasma concentrations of total PB2452, unbound PB2452, total Ticagrelor, total TAM, unbound Ticagrelor, and unbound TAM, will be assessed at predetermined timepoints.

The following PK parameters for PB2452 will be assessed. Other PK parameters may be assessed depending on the availability of data.

- Observed maximum plasma concentration (C_{max})
- Area under the plasma concentration versus time curve (AUC) from time zero to the time of the last quantifiable concentration (AUC_{0-last})
- Time to reach the observed maximum plasma concentration (T_{max})
- AUC from time zero to 24 hours post-dose (AUC_{0-24})
- AUC from time zero to 48 hours post-dose (AUC_{0-48})
- AUC from time zero extrapolated to infinity ($AUC_{0-\infty}$; if data permit)
- Terminal elimination half-life ($t_{1/2}$; if data permit)
- Clearance (CL; if data permit)
- Volume of distribution (Vd)

PK parameters for ticagrelor/TAM to be assessed are:

- C_{max}
- AUC_{0-last}
- T_{max}
- AUC_{0-24}
- AUC_{0-48}
- Area under the plasma concentration versus time curve from time zero to the end of the dosing interval (AUC_{0-tau})
- $t_{1/2}$; if data permit

- Pooled urine samples to assess urine PB2452, ticagrelor, and TAM concentrations will be collected according to predefined intervals. PK parameters for PB2452, ticagrelor, and TAM concentrations in urine for all subjects in the PK population to be calculated include:

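### SAP 11's single set of BLQ rules does not settle how unbound ticagrelor/TAM that is suppressed and then returns in the PB2452 arm enters the PK parameters, and two of three readings give a wrong AUC

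*SAP*

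**What the plan says.** SAP 11, under plasma pharmacokinetic parameters, covers the analytes together: "Plasma pharmacokinetic parameters of PB2452, ticagrelor, and TAM will be determined using noncompartmental models". The BLQ rules follow, with no exception by analyte:

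- Base rule and first exception: "BLQ values will be treated as zero with the exception that a BLQ value between 2 quantifiable concentrations will be set as missing".
- Second exception, for two or more consecutive BLQ values: when these are "followed by quantifiable concentrations in the terminal phase, those concentrations after BLQ concentrations will be treated as missing".
- Nothing is filled in for a value that has been set to missing.

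The terminal phase is found by log-linear regression. It is invalid with fewer than 3 points, a positive slope, or an adjusted r² of 0.8 or less. No trapezoid method is named.

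SAP 3.2 plans unbound as well as total concentrations: "Plasma concentrations of total PB2452, unbound PB2452, total Ticagrelor, total TAM, unbound Ticagrelor, and unbound TAM, will be assessed at predetermined timepoints". Its parameter list for ticagrelor/TAM (Cmax, AUC0-last, Tmax, AUC0-24, AUC0-48, AUC0-tau, t1/2) does not say whether total, unbound or both are meant. SAP 6.3 refers the handling of missing PK data to a Section 9.5, but Section 9 ends at 9.3.

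**The concern.** The two exceptions are built for a drug that rises, falls and stays down. There, a quantifiable value after several BLQ values is probably noise, and a BLQ value between two quantifiable ones is probably an assay failure.

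Unbound ticagrelor and TAM under PB2452 should behave differently. Infusion starts at peak ticagrelor, so Hour 0 should be quantifiable. Protocol 2.1.3 states that "PB2452 rapidly neutralizes the unbound plasma fraction of ticagrelor and TAM". Protocol 2.1.2.2 reports for the 18 g regimen that "Significant reversal was observed by 5 minutes after initiation of infusion and was sustained for 20-24 hours". Sampling continues at 20, 24, 36 and 48 h, so the late samples may show free drug coming back. Here the BLQ run is the drug effect and the later values are real.

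Free drug is the link between PB2452 and platelet function. If unbound AUCs are reported, the same data could show almost no exposure to 48 h or little reduction against placebo, depending on how the rule is read. Placebo profiles simply decline, so the distortion would sit in one arm.

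**Working it through.** The plan gives no figure on this point, so there is none to reproduce. The check applies each reading to one assumed profile.

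**From the documents.** Sampling times (SAP Table 1 footnotes): Hour 0; 5, 10 and 30 min; 1, 2, 4, 8, 12, 20, 24, 36 and 48 h. A return first seen at 20 h follows 8 suppressed samples; one first seen at 24 h follows 9.

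**Assumed.** Hour 0 level = 1. Placebo level = 0.5^(t/h), with half-life h = 6, 8 or 12 h. LLOQ = 1% or 3% of the Hour 0 level. PB2452 arm BLQ from 5 min until a return at 20, 24 or 36 h, at 25%, 50% or 100% of the concurrent placebo level. Central case: h = 8 h, return at 24 h at 50%, LLOQ 1%.

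**Central-case values.** Placebo is 0.125, 0.0442 and 0.0156 at 24, 36 and 48 h. Linear trapezoids over all samples give AUC0-24 = 10.23. Adding 6 × (0.125 + 0.0442) + 6 × (0.0442 + 0.0156) = 1.37 gives AUC0-48 = 11.61. The PB2452 arm has 1 at Hour 0, a BLQ run, 0.0625 at 24 h, 0.0221 at 36 h, and 0.0078 at 48 h (BLQ).

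**Reading A: return treated as terminal phase and deleted.** Only the first 5 minutes remain: ½ × 1 × 5/60 = 0.0417. That is 0.4% of placebo for both AUC0-24 and AUC0-48.

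**Reading B: whole BLQ run treated as missing and bridged.**
- Linear: AUC0-24 = 24 × (1 + 0.0625)/2 = 12.75, or 12.75/10.23 = 125%. AUC0-48 = 12.75 + 6 × (0.0625 + 0.0221) + 6 × 0.0221 = 13.39, or 115%.
- Linear-up/log-down: AUC0-24 = 24 × (1 − 0.0625)/ln(1/0.0625) = 8.12, or 80% of a placebo AUC computed the same way. AUC0-48 is 77%.

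**Reading C: run kept at 0, later values kept.** AUC0-24 = 0.0417 + 2 × 0.0625 = 0.167, or 1.6%. AUC0-48 = 0.167 + 0.508 + 0.133 = 0.807, or 7.0%.

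| % of placebo, all scenarios | AUC0-24 | AUC0-48 |
|---|---|---|
| A | 0.3-0.5 | 0.3-0.5 |
| B, linear | 85-195 | 72-208 |
| B, log-down | 58-100 | 51-100 |
| C | 0.3-18.6 | 1.5-35.3 |

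**When does the return qualify as terminal phase?** At least 3 quantifiable, declining points are needed. In the central case with LLOQ at 1%, only the 24 and 36 h values are quantifiable by 48 h, so the criterion is narrowly missed. With an LLOQ below 0.78% the 48 h value counts, and reading C gives 0.0417 + 0.125 + 0.508 + 6 × (0.0221 + 0.0078) = 0.854, or 7.4%. With return at 20 h (0.0884) and LLOQ 1%, three points qualify. Reading C then gives 0.0417 + 4 × 0.0884 + 2 × (0.0884 + 0.0625) + 0.508 + 0.133 = 1.337, or 11.5%, against 0.4% under A. In such subjects t1/2 is lost too, because the deleted points are those the regression would use. A return first seen at 36 h, or still rising, would not qualify. Similar subjects in one arm could therefore be handled differently.

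**Is a BLQ run plausible?** KD is 20 pmol/L and the Fab is 47.4 kDa (Protocol 2.1.2 and 2.1.3); the bolus is 6 g. In an assumed 3-10 L, Fab is 6/(47,400 × V) = 42 to 13 µmol/L. Assumed total ticagrelor of 500-5000 ng/mL, at an assumed 523 g/mol, is 0.96-9.6 µmol/L. At equilibrium, free drug ≈ KD × D/(F − D), with D = total drug and F = total Fab. This runs from about 0.46 pmol/L (0.2 pg/mL) to about 62 pmol/L (32 pg/mL). TAM, which shares the binding, is left out; including it would raise the upper end.

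**The case against.** The strongest reply is that SAP 11 already permits the sensible result. Its base rule is zero, its first exception speaks of one BLQ value rather than a run, and its second applies only in the terminal phase. Free drug still rising as PB2452 clears is not an elimination phase. If neither exception applies, reading C follows. This stands as a possible reading, but the SAP does not say it is the intended one, and a return that declines over three or four samples can meet its own terminal-phase criteria.

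Other parts of the reply also stand:

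- Unbound parameters are not shown to be planned; only unbound concentrations are.
- No LLOQ is given. Protocol 2.1.3.3 reports that free drug in the rat study was inconsistent, quantifiable at follow-up and no different between groups, which it attributes to the assay. The 20-24 h figure describes platelet reversal, not free drug.
- The exceptions govern parameters only. Concentrations are still listed and plotted by subject and summarised with BLQ as zero, so suppression and return stay visible.
- Total ticagrelor and TAM rise after PB2452 (Protocol 2.1.4.1), so they do not show this pattern.
- PK is summarised descriptively, with no between-arm test.

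A reader might infer that unbound AUCs in the PB2452 arm will come out near zero or as high as placebo, and that the offset of reversal will be hidden. The documents do not support this. It needs the unstated conditions above and leaves out reading C. A near-zero AUC0-24 is also largely true drug effect (0.4% against 1.6% in the central case), and bridging reaches or exceeds placebo in only some scenarios.

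**Conclusion.** The point holds as a conditional defect. If parameters are derived for unbound ticagrelor/TAM and the suppressed samples are BLQ, SAP 11 can delete real returning concentrations or bridge the reversal period, and nothing in it secures the sensible handling. The deletion is a stated rule without an analyte exception, so this is more than missing detail.

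Under the assumed central profile, AUC0-48 is 0.4% of placebo with deletion, 77% (log-down) or 115% (linear) with bridging, and 7.0% with zeros and later values both kept. Across scenarios bridging spans roughly 50-200%. These sizes rest on the assumed half-life, LLOQ, return time and return level. The 0.4% also requires the return to be classed as terminal phase, which in the central case needs an LLOQ slightly below the assumed 1%.

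The effect is confined to descriptive secondary PK parameters for unbound analytes in the PB2452 arm. Concentration listings, summaries and plots, total ticagrelor/TAM and the primary PRU test are unaffected. It is worth settling before database lock, so that the choice between such different answers is not made after unblinding.

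**What to change.** In SAP 11:

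1. State whether PK parameters are derived for unbound ticagrelor and unbound TAM.
2. If so, for those analytes set any run of two or more consecutive BLQ values after the start of infusion to 0, with LLOQ/2 as a sensitivity analysis. Keep all later quantifiable concentrations in AUC0-24, AUC0-48 and AUC0-last, and in the terminal fit where SAP 11's validity criteria are met.
3. Keep the missing rule for a single isolated BLQ value between two quantifiable ones. Setting every post-infusion BLQ to zero would put false zeros into placebo profiles.
4. Name the trapezoid method.

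Correct the SAP 6.3 reference to Section 9.5 at the same time. The cost is a few SAP sentences and one analyte-specific setting in the PK program, with no new data.
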